#### 11.10 INTERIM ANALYSIS

No interim analysis is planned for this study.

#### 11.11 SAMPLE SIZE DETERMINATION

The primary efficacy endpoint is the mean change from baseline in hepatic fat content assessed by MRI-PDFF at Week 24/EOT in participants with NAFLD. In a previously conducted Phase 2 study in NAFLD participants, the mean change from baseline in hepatic fat content at Week 16 in Saroglitazar 4 mg group was -4.2 (SD=6.2) and in Placebo was -0.3 (SD=5.7).

Approved by: [name] No.: SARO.20.001
[name]	Version No.: 4.0

#### CONFIDENTIAL Page 71 of 109

Assuming a similar treatment effect on hepatic fat content in Saroglitazar 4 mg group at Week 24/EOT in this study, a sample size of 102 participants (51 participants in each treatment arm) will provide 80% power to detect a treatment difference of at least 3 in change from baseline in hepatic fat content at Week 24 between Saroglitazar 4 mg and Placebo using a one-sided 5% level of significance based on two-sided t-test, assuming a common standard deviation of 6.

Assuming a dropout rate of 15% at week 24, approximately 120 participants (60 participants in each treatment arm) will be randomized in a 1:1 ratio to receive either Saroglitazar 4 mg or placebo.

#### 11.12 COVID-19 CONSIDERATIONS

Given the current COVID-19 pandemic, per regulatory guidance, a listing of participants either experiencing COVID-19 infection or at least possibly affected by COVID-19 related measures will be produced where applicable. Further details relating to additional populations and subgroup analyses, handling of protocol deviations, handling of missing data (including use of virtual assessments and/or switches from local to centralized labs), and any other considerations related to COVID-19 infection and related measures will be detailed further in the SAP, finalized before unblinding.

Approved by: [name] No.: SARO.20.001
[name] Version No.: 4.0

CONFIDENTIAL Page 72 of 109

#### 12. ADMINISTRATIVE MATTERS

The study will be carried out in compliance with the protocol, in accordance with the ICH GCP and other applicable regulatory guidelines.

#### **12.1 ETHICS**

#### 12.1.1 Institutional Committee Review and Communications

The investigator (or sponsor as appropriate according to local regulations) will submit this protocol, informed consent, and any accompanying material to be provided to the participant to the IRB. The trial will not be initiated before the protocol and informed consent, and any accompanying material have been reviewed and have received approval/favorable opinion from the IRB. The study will use a single IRB (sIRB) for its IRB of record. Each site and the sIRB will have a fully signed IRB Authorization Agreement (IAA) in place for the duration of the study. Should a protocol amendment be written that requires IRB approval, the changes in the protocol will not be instituted until the amendment and revised informed consent (if appropriate) has been reviewed and received approval/favorable opinion from the sIRB. A protocol amendment intended to eliminate an apparent immediate hazard to participants may be implemented immediately providing that the appropriate regulatory authorities and sIRB are notified as soon as possible and an approval is requested. Protocol amendments only for logistical or administrative changes may be implemented immediately; however, both the sIRB and the Regulatory Authorities will be notified as soon as possible.

The constitution of the IRB must comply with the requirements of the US Code of Federal Regulations (CFRs) or applicable regulatory agency. A list of the IRB members, with names and qualifications, will be requested. If such a list is unavailable, the investigator or designee must provide the name and address of the IRB along with a statement from the IRB that it is organized according to GCP and the applicable laws and regulations. The IRB must also perform all duties outlined by the requirements of the regulatory agencies.

#### 12.1.2 Informed Consent and Participant Information

Prior to participation in the study, written informed consent will be obtained from each participant (or the participant's legally accepted representative) according to the regulatory and legal requirements of the participating site. Virtual verbal consent may be allowed at certain sites per IRB approval with signatures obtained at the first screening visit. Each signature must be dated by each signatory. The informed consent and all study data forms will be retained by the investigator or designee as part of the study records. A signed copy of the informed consent and recruitment materials must be given to each participant or the participant's legally authorized representative.

A written informed consent will also be obtained from each participant for the optional banking assessments. A legally accepted representative of the participant is not permitted to consent for the optional banking assessments.

Approved by: [name] No.: SARO.20.001
[name]	Version No.: 4.0

#### CONFIDENTIAL Page 73 of 109

The participant must be informed that his/her medical records may be examined by authorized monitors or Clinical Quality auditors appointed by the sponsor, by appropriate IRB members and by inspectors from regulatory authorities.

Should a protocol amendment be made, the participant informed consent form and recruitment materials may need to be revised to reflect the changes to the protocol. It is the responsibility of the investigator to ensure that an amended consent form is reviewed and has received approval/favorable opinion from the IRB and that it is signed by all participants subsequently entered in the study and those currently in the study, if affected by the amendment.

#### 12.1.3 Compensation and Insurance

Participants will not be required to pay for the study medications and laboratory investigations, if they participate in this study. If the participants develop a medical condition as a result of participation in this study, including SAEs, he/she will receive emergency care; out-patient care or hospitalization including proper referral, as needed. Zydus Therapeutics Inc. is the sponsor of the study and has an insurance cover, which will pay the medical expenses for the treatment of such conditions. This insurance covers damages or injury or death resulting from participation in a study and which are mentioned during the participation in the study. Any injury or damages or death will be reported to the insurer. Participants should report any discomforts, problems, or research related injuries immediately to study Investigator or study staff. In case of injury occurring to participants during the clinical trial as a result of taking the study drug(s) or from the procedures done for the purpose of this study, the sponsor will pay for those medical expenses necessary to treat the injury that are not covered by the participant's medical insurance or any other third-party coverage.

#### 12.2 RECORD KEEPING 12.2.1 Drug Accountability

Drug supplies, which will be provided by the sponsor, must be kept in a secure, controlled access storage area under the storage conditions defined by the sponsor. A temperature log must be maintained to make certain that the drug supplies are stored at the correct temperature.

The investigator/designee and/or pharmacist must maintain records of the product's delivery to the study site, the inventory at the site, the dispensation to each participant and the return to the sponsor or alternative disposition of unused product(s). These records will include dates, quantities, batch/serial numbers, expiration dates (if applicable) and the unique code numbers assigned to the IP(s) and study participants. The investigator or designee will maintain records, that document adequately, that the participants were provided the doses specified by the protocol and reconcile all IP(s) received from the sponsor. At the time of return to the sponsor, the investigator or designee must verify that all unused or partially used drug supplies have been returned by the study participants and that no remaining supplies are in the investigator's or site's possession.

Approved by: [name] No.: SARO.20.001
[name]	Version No.: 4.0

CONFIDENTIAL Page 74 of 109

#### 12.2.2 Emergency Code Break (Unblinding)

An emergency code break will be available to the Investigator and/or pharmacist. This code break must only be opened in emergency situations when the identity of the study medication must be known by the Investigator in order to provide appropriate medical treatment. If the code break for a participant is opened, Sponsor must be informed immediately. The reason for opening the code break must be documented along with the date and the initials of the person who broke the code. Participants whose treatment assignment becomes unblinded inadvertently, need not require to complete the scheduled evaluations and the participant will be withdrawn from the trial from that visit.

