#### 7.4 PARTICIPANT WITHDRAWAL

A participant may withdraw from the study at any time without penalty and for any reason without prejudice to her/his future medical care. Although a participant is not obliged to give his/her reason for withdrawing prematurely, the investigator will make a reasonable effort to obtain the reason while fully respecting the participant's rights. If there is a medical reason for withdrawal, the participant will remain under the supervision of the investigator for follow-up of AE(s) as detailed in Section 12.4.1.6.

Every effort will be made to continue clinical and/or laboratory follow-up, as appropriate, in participants who wish to withdraw from the study medication, and reasonable efforts will be made to contact a participant who fails to attend any follow-up appointments, in order to ensure that he/she is in satisfactory health. A participant's withdrawal of consent and agreement to undergo a final examination will be documented on the case report form (CRF) and on the investigator's copy of the informed consent form (ICF), which will be countersigned and dated by the participant. Safety follow-up within 4 weeks from the date of withdrawal will be conducted for all participants who receive the study medication but do not complete the study according to the study protocol.

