#### 10. INVESTIGATIONAL PLAN 10.1 TRIAL DESIGN AND PLAN

This phase 2a study is a randomized, placebo-controlled, double-blind, multicenter, parallel-arm trial to evaluate the safety and efficacy of Saroglitazar Magnesium 4 mg compared with placebo in NAFLD in PLWH. Eligible participants will be randomized in a 1:1 ratio to receive Saroglitazar Magnesium 4 mg or placebo. This study plans to enroll approximately 120 PLWH with NAFLD from within the catchment area of approximately 8 participating clinical centers or community HIV practices in US. The study will be conducted over a period of 36 weeks, including upto 8-week screening period, 24-week treatment period and 4-week safety follow-up period (Figure 1 and Section 2 Schedule of Assessments). Participants will be evaluated at the study sites for 10 scheduled visits.

- Screening: Week -8 (Visit 1) and Week -6 (Visit 2); Screening period will last up to 8 weeks. Visit 2 must occur at least 14 days after Visit 1.
- Randomization: Day 1 (Visit 3) can occur at any time point after visit 2 but within 8 weeks of screening period and participant can be randomized upon confirmation of eligibility criteria.
- Treatment Period: Week 0 (Visit 3), Week 2 (Visit 4), Week 4 (Visit 5), Week 8 (Visit 6), Week 12 (Visit 7), Week 16 (Visit 8), Week 24/EOT (Visit 9)
- Safety Follow-up: Week 28 (Visit 10)

Eligibility of subject will be confirmed as per local reading of MRI-PDFF. Baseline and Week 24/EOT MRI-PDFF assessment for Primary endpoint will be read by central laboratory. Details will be mentioned in Imaging manual. All laboratory investigations will be performed with at least 8-hours fasting blood samples. Participants will be monitored during the study at every visit for development of any AEs, including treatment emergent AEs and DILI.

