#### 10.2.5 Early Termination (ET) visit

Participants prematurely discontinued from the study would be encouraged to complete an ET visit within 30 days of last dose. The investigator should make every effort to perform following assessments at the early termination visit in case if any participant discontinues from

Approved by: [name] No.: SARO.20.001
[name]	Version No.: 4.0

#### CONFIDENTIAL Page 60 of 109

the study prior to completion of his/her study treatment period (i.e. termination prior to Week 24 visit):

- Complete physical examination
- Vital signs measurement.
- AE assessment.
- Concomitant medication review
- Monitoring of diet, exercise, avoidance of alcohol, and other hepatotoxic agents (Refer Appendix 8).
- Compliance review for study medication
- Weight, Hip and waist minimal circumference measurements
- Fasting Laboratory evaluations
- Serum pregnancy test for all female participants of child bearing potential.

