#### 10.6 PROTOCOL DEVIATIONS

For the purposes of this study, no distinction will be made between protocol violation and deviation. Deviation may be categorized as minor protocol deviation or major protocol deviation. Classification of protocol deviations as major or minor will be assessed at the blinded data review meeting prior to database lock. Minor protocol deviation includes any deviation that do not necessarily influence the results/outcome of primary endpoints or participant safety. Minor protocol deviation does not require immediate notification to the IRB unless otherwise specified by IRB requirements. All minor protocol deviations will be noted in monitoring reports and discuss with investigator/site personal. Major protocol deviation includes any violation, which may influence the results/outcome of primary endpoints or participant safety. Major protocol deviation must be reported immediately to the IRB, as specified by the IRB requirements. All major protocol deviations will be reported to the sponsor immediately (Note: persistent non-compliance of minor protocol deviations may rise to the level of major protocol deviations). As a result of protocol deviations, corrective actions are to be developed and implemented promptly.

The sponsor reserves the right to terminate the study at a given center in the event of monitoring and/or auditing findings of serious or persistent non-compliance with the protocol, Standard Operating Procedures (SOPs), GCP, and/or applicable regulatory requirement(s) by an investigator/Institution. In all cases of site closure due to protocol deviations, the IRB and regulatory authority will be informed. The clinical study report (CSR) will provide a list of protocol deviations/violations in a separate section. The results will be analyzed for all participants regardless of protocol deviation occurrence.

Protocol deviations/violations will include but are not limited to the following:

- Violations of inclusion and exclusion criteria at randomization.
- Participants who met the withdrawal criteria but were not withdrawn.
- Participants who received the wrong treatment or incorrect dose.
- Participants who received an excluded medication.
- Serious non-compliance with regulatory or GCP guidelines.

Approved by: [name] No.: SARO.20.001
[name]	Version No.: 4.0

#### CONFIDENTIAL Page 62 of 109

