#### • For the primary estimand:

- Composite strategy: missing data will be handled by imputing using the worst outcome of MRI-PDFF across either treatment arm.
  - o Treatment policy strategy: available data occurring on or after the ICE will be analyzed as observed. Any missing Week 24 MRI-PDFF data due to discontinuation of study treatment for reason other than AE, lack of efficacy (LoE), liver transplant, hepatic decompensation or bariatric intervention will be multiple imputed using a missing at random (MAR) approach.
- For the secondary estimand:
- Composite variable strategy: missing data will be handled by imputing using the worst outcome of MRI PDFF across either treatment arm.

Approved by: [name] No.: SARO.20.001
[name]	Version No.: 4.0

#### CONFIDENTIAL Page 65 of 109

O Hypothetical strategy: the approach allows for the assessment of the treatment effect in an alternative, hypothetical setting where 1) all participants take the assigned study treatment without discontinuation/interruption, and 2) prohibited medication was not available to participants for the study duration. Available data occurring on or after the ICE will be set to missing, and multiple imputed by a MNAR application of SAS Proc MI based on the distribution of data for each treatment arm where all participants do not experience an ICE.

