#### 11.5.6 Handling of Missing Data

Every effort will be made to prevent participants early terminating the study and for participants who discontinue study drug, every effort will be made to continue to collect data after

Approved by: [name] No.: SARO.20.001
[name]	Version No.: 4.0

### CONFIDENTIAL Page 66 of 109

discontinuation. Where missing data exist for primary and secondary efficacy endpoints, imputation will occur where specified.

The primary method of imputation for missing data will be MI (Multiple Imputation); the MI procedure of the SAS system will be used to generate sets of data with missing values imputed from observed data. It is expected that the pattern of missing data will be monotonic, as the biopsy will be performed only at screening and at Week 24/EOT visits.

A logistic regression model will be used for the ordinal scores and linear regression will be used for the continuous variable.

The imputed datasets will be analyzed using the methodology described in Section 11.5. The results from the analysis of the multiple imputed datasets will be combined by the MIANALYZE procedure of the SAS system. The number of imputations and the seed to be used, plus any further details required, will be detailed in the SAP.

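### Protocol Section 12.2.2 withdraws inadvertently unblinded participants and waives their evaluations, so anyone affected before Week 24 has no primary endpoint value: avoidable missing data, at odds with the treatment-policy estimand

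*Protocol*

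**What the plan says.** **Unblinding.** Protocol Section 12.2.2 first covers deliberate emergency code breaks. Its last sentence deals with inadvertent unblinding only: such participants "need not require to complete the scheduled evaluations and the participant will be withdrawn from the trial from that visit". Section 8.5 describes deliberate unblinding for a SUSAR or a medical emergency and attaches no withdrawal to it.

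**When the endpoint is measured.** Section 10.2 lists MRI-PDFF at Visit 1 and at Visit 9 (Week 24/EOT) only. Under Section 10.2.5, participants who leave early "would be encouraged to complete an ET visit within 30 days of last dose", and the assessments listed for that visit do not include MRI-PDFF. Section 10.1 adds: "Baseline and Week 24/EOT MRI-PDFF assessment for Primary endpoint will be read by central laboratory".

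**What the analysis expects.** For the treatment-policy strategy of the primary estimand, Section 11.5.2.2 says "available data occurring on or after the ICE will be analyzed as observed". Section 11.5.6 says that "for participants who discontinue study drug, every effort will be made to continue to collect data after" discontinuation. Section 10.6 says "The results will be analyzed for all participants regardless of protocol deviation occurrence".

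**Safety after withdrawal.** Section 7.4 says "Safety follow-up within 4 weeks from the date of withdrawal will be conducted for all participants who receive the study medication" and do not complete the study. Section 10.2.4 makes Week 28 (Visit 10) the scheduled safety follow-up visit.

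**The concern.** Accidental disclosure of an assignment is an error in trial conduct. It tells us nothing about how the participant responded, and it is not among the intercurrent events in Section 11.5.1. Yet Section 12.2.2 ends that participant's evaluations. Someone who stops study drug is to be followed and measured; someone who has only lost the blind is not.

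At stake are primary endpoint values that could have been collected, and which the estimand would have used as observed. A second issue is that sites receive instructions on follow-up after withdrawal that do not fit together cleanly.

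**Working it through.** **Step 1. Does the rule remove the endpoint?** The sections, side by side:

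| Section | Content | Consequence for inadvertent unblinding before Week 24 |
|---|---|---|
| 12.2.2 | Evaluations waived, withdrawal from that visit | No Week 24 visit |
| 10.2 visit lists | MRI-PDFF at Visit 1 and Visit 9 only | No intermediate scan to fall back on |
| 10.2.5 | ET visit encouraged; no MRI-PDFF listed | No replacement scan |
| 11.5.2.2 | Post-event data used as observed; missing Week 24 values after stopping drug for reasons other than AE, lack of efficacy and similar are multiply imputed under MAR | The value is imputed instead of measured |
| 10.6 and 11.3 | Analysed regardless of deviations; any dosed randomized participant is in ITT | In the analysis set, without an outcome |

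The participant stays in the ITT analysis but the outcome is not collected. The Section 2 schedule table cannot be read in the public copy, so this rests on the visit lists in Section 10.2.

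**Step 2. Does it clash with Section 7.4?** Section 7.4 applies after withdrawal, so a site could waive the remaining visits and still carry out a safety contact within 4 weeks. However, Week 28 is one of the scheduled visits, and the waiver in Section 12.2.2 makes no exception for safety visits. The two sections are in tension and need reconciling; they are not strictly incompatible.

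**Step 3. Reproduce the plan's sample size (Section 11.11).** Inputs: difference 3, SD 6, one-sided alpha 0.05, power 80%, 51 per arm, 15% dropout.

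- Noncentrality = 3 / (6 × √(2/n)); degrees of freedom = 2n − 2; power = P(noncentral t > one-sided 5% critical value).
- n = 51: noncentrality 3 / (6 × 0.1980) = 2.525, power 80.6%.
- Dropout: 102 / 0.85 = 120.

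Both stated figures, 102 evaluable and 120 randomized, reproduce.

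**Step 4. Cost of extra losses.** The documents give no rate of inadvertent unblinding. The losses below are assumed, equal in the two arms, added to the 15% allowance, and analysed as complete cases.

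| Extra losses per arm | Evaluable per arm | Noncentrality | Power |
|---|---|---|---|
| 0 | 51 | 2.525 | 80.6% |
| 1 | 50 | 2.500 | 79.9% |
| 3 | 48 | 2.449 | 78.4% |

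The plan imputes, so complete-case power is an approximation. With no scan between baseline and Week 24, imputation has no intermediate value of the endpoint to draw on.

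**The case against.** Several arguments on the other side stand.

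- **Safety follow-up.** A reader might infer that a site cannot obey both 12.2.2 and 7.4, or that all safety data stop at unblinding. The documents do not support either. Section 7.4 is triggered by withdrawal, Section 10.2.5 offers an ET visit with adverse event and laboratory assessments, and Section 12.4.1.6 follows adverse events to resolution or a similar end.
- **Central reading.** A reader might infer that a centrally read scan cannot be affected by the participant's knowledge of the arm. Central reading protects the measurement from the site. It does not stop a participant from changing diet, weight or adherence, or an investigator from changing permitted co-medication (Section 8.8.2), and each of these could alter liver fat. Section 10.1 also does not say whether the central reader is blinded. Keeping these participants therefore carries some risk of bias.
- **Informative loss.** A reader might infer that code breaks cluster around adverse events and so differ by arm. Breaks of that kind are the deliberate ones, which the challenged sentence does not cover. Nothing in the documents links accidental disclosure to outcome.
- **Grounds for withdrawal.** Unblinding is not named in Section 7.6.2, but item 2 there (major deviations that may influence the primary endpoint) could be read to include it. Section 10.4 also allows withdrawal for serious deviations.
- **Continued data collection.** Section 11.5.6 speaks of people who stop study drug, which is not the same as withdrawal from the trial. The mismatch is with its aim more than its letter.
- **Power.** A 15% dropout allowance already exists, and some of these withdrawals might fall within it.

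These arguments narrow the point but do not remove it. None of them gives a reason not to obtain the Week 24 scan. The possible bias from knowing the arm can be examined once the scan has been taken, but not if it never was.

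**Conclusion.** The point holds as one of avoidable missing data and inconsistent rules. Following Section 12.2.2 before Week 24 leaves no primary endpoint value for a participant whom the analysis still intends to include, and the sentence does not fit well with Sections 7.4, 10.6, 11.5.2.2 and 11.5.6.

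The size is probably small. One extra loss per arm moves power from 80.6% to 79.9%, and three per arm to 78.4%. These counts are assumptions, and it would be wrong to conclude from them that the trial is materially underpowered. Bias from the loss is possible but not demonstrated.

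The SAP reports that the study was terminated with four participants randomized and no primary endpoint data, so no efficacy result is affected. It states that no unblinding took place for a safety reason and does not mention inadvertent unblinding. The point matters for the design, and for any later protocol that reuses this text. It is a cheap improvement, of minor to moderate severity.

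**What to change.** Replace the last sentence of Section 12.2.2 with text to this effect:

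> Inadvertent unblinding of a participant's assignment is recorded as a protocol deviation. Unless consent is withdrawn, the participant continues all scheduled evaluations, including the Week 24 MRI-PDFF and the Week 28 safety visit, and remains in the ITT population. Such participants are flagged, and the primary analysis is repeated without them as a sensitivity analysis.

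Reconcile Section 12.2.2 with Sections 7.4, 7.6.2 and 11.5.6 so that withdrawal, follow-up and data collection read as one rule. The change concerns evaluations and analysis only. It sets no rule on study drug and does not extend to deliberate emergency code breaks.

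**Cost.** One replaced sentence, cross-references, one data flag and one extra analysis. The drawback is that knowledge of the arm may colour SF-36 and adverse event reports, and may also influence diet, weight, adherence or co-medication and hence liver fat. The sensitivity analysis shows how far the result depends on these participants.
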